7.4.2.8 Rate of progression of CKD measured by annualized eGFR slope over time

Geometric Mean (GM) and coefficient of variation (CV) will be displayed for eGFR. In addition, change from baseline and 95% CI will be presented.

The annualized eGFR slope over time (expressed in ml/min per 1.73 m² or % per year) will be determined using the SAS code below:

```
proc mixed data=egfr2;
class usubjid strata_except_egfr_hb TRTPN TRTP;
model aval= strata_except_egfr_hb HGBBL atptn
HGBBL*atptn egfrbl*atptn atptn*TRTPN*TRTP
atptn*strata_except_egfr_Hb / solution ddfm=kr
outpredm=pred cl;
random intercept atptn / subject=usubjid type=un ;
estimate 'Annualized slope Roxadustat'
intercept 0
strata_except_egfr_hb 0 0 0 0
HGBBL 0
atptn 1
HGBBL*atptn &meanHbBase
egfrbl*atptn &mean egfrbl
atptn*TRTPN*TRTP 1 0
atptn*strata_except_egfr_Hb &prop_strata
/cl;
estimate 'Annualized slope Placebo'
intercept 0
strata_except_egfr_hb 0 0 0 0
HGBBL 0
atptn 1
HGBBL*atptn &meanHbBase
egfrbl*atptn &mean egfrbl
atptn*TRTPN*TRTP 0 1
atptn*strata_except_egfr_Hb &prop_strata
/cl;
ods output lsmeans=lsmeans_un estimates=est_un;
ods output FitStatistics=FitStatistics SolutionF=SolutionF;
run;
```

Annualized eGFR slope over time is estimated by a random slopes and intercepts model using all available eGFR values (one baseline and all post-treatment values up to End of Treatment Period or start of dialysis) adjusted on Baseline Hb, Region, CV history at

Baseline and the interaction terms (Baseline eGFR by timepoint and Baseline Hb by timepoint). All assessments collected after initiation of acute or chronic dialysis will be excluded from the analysis.

Superiority will be declared if the lower bound of the two-sided 95% confidence interval of the difference in Least Square Means between roxadustat and placebo is above 0.

Model checking:

Residual plots will be produced showing the following:

- Model residuals in the y-axis and model predictions in the x-axis,
- Model residuals in the y-axis and baseline Hb in the x-axis.

Different dot styles will be used for the two treatment arms. Solid black symbols (square) will be used for roxadustat and non-solid red symbols (X) will be used for placebo.

If the residual diagnostics show heteroscedasticity, additional analysis will be performed where annualized eGFR slope over time (% per year) is estimated by a random slopes and intercepts model using all available (log-transformed) eGFR values (one baseline and all post-treatment values up to End of Treatment Period or start of dialysis) adjusted on Baseline Hb, Region, CV history at Baseline and the interaction terms (Baseline log(eGFR) by timepoint and Baseline Hb by timepoint).

Least Square Means will be transformed back to the original scale and expressed as annual percent changes.

7.4.2.9 Additional Analyses of the Key Secondary Endpoints

Each of these key secondary endpoints will also be analyzed by the subgroups of interest defined in Section 7.8 using only the primary analysis method, descriptively (no hypothesis testing).

Table 24 Additional Analyses of the Key Secondary Endpoints

Code	Set	Endpoint	Method	Covariates
A1	FAS	Change to the Average Hb in weeks 28-36 (without rescue therapy) by Subgroup	MMRM	Region, History of CV, visits and visits by treatment as categorical variables. BL Hb and BL eGFR as continuous covariates.
A2	FAS	Change from baseline to the Average LDL in weeks 12-28 by Subgroup	MMRM	Region, History of CV, visits and visits by treatment as categorical variables. BL LDL, BL Hb and BL eGFR as continuous covariates.
A3	FAS	SF36-PF Change from Baseline at Weeks 12-28 for all subjects by Subgroup	MMRM	Region, History of CV, visits and visits by treatment as categorical variables. BL Hb, BL SF-36-PF subscore and BL eGFR as continuous covariates.

Table continued on next page

Code	Set	Endpoint	Method	Covariates
A4	FAS	SF36-VT Change from Baseline at Week 28 for all subjects by Subgroup	MMRM	Region, History of CV, visits and visits by treatment as categorical variables. BL Hb , BL SF-36-VT subscore and BL eGFR as continuous covariates.
A5	PPS	Change from baseline to the Average MAP in weeks 20-28 by Subgroup	MMRM	Region, History of CV, visits and visits by treatment as categorical variables. BL MAP, BL Hb and BL eGFR as continuous covariates.
A6	PPS	time to first occurrence of hypertension by Subgroup	Cox regression + Kaplan Meier	Stratified on Region, History of CV and adjusted on BL Hb, BL eGFR as continuous covariates

* Subgroup: (1) age, (2) sex, (3) region, (4) baseline hemoglobin category, (5) history of CV (6) Baseline eGFR category (7) Baseline CRP category [only for A1] and (8) Baseline Iron Repletion Status category [only for A1]

Forest plots will be produced where all subgroup factors will appear in the y-axis and the appropriate statistic comparing roxadustat to placebo and the 95% confidence interval will appear in the x-axis.

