7.4.2.2 Secondary Analysis

Each of the key secondary endpoints will be repeated separately by gender, age group, region, BL Hb categories, iron repletion at BL, diabetes and eGFR categories. Subgroup analyses will be detailed in the SAP.

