All available SF-36 VT values will be used i.e., both scheduled and unscheduled SF-36 VT values. SF-36 PF values in analysis visit windows at weeks 12 and 28 will be selected for the calculation of the average VT sub-score of weeks 12 to 28 (see [Table 32](#) and Section [7.11.4](#) for the analysis windows definition and the differentiation between the MMRM and ANCOVA analyses).

For missing SF-36 VT, refer to Section [7.11.1](#) for the imputation rules. Baseline assessment is the assessment from Day 1 visit.

6.1.2.5 Change from BL in SF-36 Physical Functioning (PF) Sub-score to the Average PF Sub-score of Weeks 12 to 28

For details on the SF-36 PF subscore, refer to Section [6.1.3.14.1](#). Similar rules as for Section [6.1.2.4](#) will be used for the calculation of the SF-36 VT scale sub-score.

6.1.2.6 Change from BL in Mean Arterial Pressure (MAP) to the Average MAP Value of Weeks 20 to 28

Blood pressure will be measured singly for the three visits during the screening period and in triplicate with a 2-minute interval for all other visits during the study. During the study, for systolic blood pressure (SBP) and diastolic blood pressure (DBP), the average will be calculated for each visit using the three readings. If less than three readings are available, all will be used in the calculation of the average.

MAP will be derived for each visit from the above averaged SBP and the DBP using the following equation:

$$\text{MAP} = (2/3) * \text{DBP} + (1/3) * \text{SBP}$$

All available MAP values during the Safety Emergent Period will be used, i.e. both scheduled and unscheduled MAP values. MAP values in analysis visit windows at weeks 20, 22, 24 and 28 will be selected for the calculation of the average MAP during weeks 20-28 (see [Table 31](#) and Section [7.11.4](#) for the analysis windows definition and the differentiation between the MMRM and ANCOVA analyses).

For missing data imputation rules, refer to Section [7.11.1](#). Baseline assessment is the assessment on Day 1 (average of the three readings). If the baseline assessment is missing, then the latest available value prior to first drug administration will be used.

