7.4.2 Analysis of Key Secondary Endpoints

The primary analysis set for the analysis of the key secondary endpoints will be the PPS for the non-inferiority tests and the FAS for the superiority tests.

All inferential analyses will evaluate the difference between the treatment arms: roxadustat versus placebo.

Once the primary hypothesis has been rejected for the EU (EMA) primary endpoint, the key secondary endpoints will be tested using a fixed sequence testing procedure, as depicted in Table 16 in order to maintain the overall two-sided type I error rate at 0.05. If the null hypothesis is rejected for a test, the claim of superiority (or non-inferiority) will be

considered successful and the test will progress to the next comparison in sequence as follows:

Table 16 Key Secondary Endpoints fixed sequence testing procedure

Test	Analysis set	Endpoint	Comparison
1	FAS	Hb change from BL to the average Hb in weeks 28-36, without having received rescue therapy within 6 weeks prior to and during this 8-week evaluation period.	Superiority of roxadustat versus placebo
2	FAS	Change from BL in Low Density Lipoprotein (LDL) cholesterol to the average LDL cholesterol of weeks 12 to 28.	Superiority of roxadustat versus placebo
3	FAS	Use and time to first use of rescue therapy during the treatment period	Superiority of roxadustat versus placebo
4	FAS	Change from BL in SF-36 Vitality (VT) sub-score to the average VT sub-score of weeks 12 to 28 for all subjects	Superiority of roxadustat versus placebo
5	FAS	Change from BL in SF-36 Physical Functioning (PF) sub-score to the average PF sub-score of weeks 12 to 28 for all subjects	Superiority of roxadustat versus placebo
6 *	PPS	Change from BL in mean arterial pressure (MAP) to the average MAP value of weeks 20 to 28.	*: Non-inferiority of roxadustat versus placebo (the non-inferiority margin for the difference between groups is fixed as 2 mmHg)
7 *	PPS	Time to first occurrence of hypertension (defined as an increase from BL of ≥ 20 mmHg systolic blood pressure (SBP) and SBP ≥ 170 mmHg or an increase from baseline of ≥ 15 mmHg diastolic blood pressure (DBP) and DBP ≥ 110 mmHg)	*: Non-inferiority of roxadustat versus placebo (the non-inferiority margin for the difference between groups is fixed as a hazard ratio of 1.3)
8 *	FAS	Rate of progression of CKD measured by annualized eGFR slope over time	*: Superiority of roxadustat versus placebo

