For the IPCW method, refer to Appendix 10.7 for details. If the conclusions of the analysis using stratified cox model and IPCW method are not concordant, additional analysis using IPCW method will be performed for each of the endpoints separately.

- Time to first use of RBC transfusion
- Time to first use of IV iron supplementation
- Time to first use of ESA

Details of these endpoints are provided in Sections 7.4.3.8, 7.4.3.9 and 7.4.3.10

7.4.2.4 Change from baseline in SF-36 VT subscore to the average in weeks 12–28

Change from baseline in VT subscore of SF-36 to the average of weeks 12–28 will be compared by treatment arm for all subjects (primary analysis) and in the subsets of subjects with baseline vitality subscore below 50 and equal or above to 50. It will be done using a MMRM method adjusting for the region, history of CV, baseline SF-36 VT subscore,

baseline Hb and baseline eGFR as covariates. Baseline SF-36 VT subscore, baseline Hb and baseline eGFR will be included as continuous variables.

The analysis will be similar to the analysis provided in Section [7.4.1.2](#) Superiority will be declared if the lower bound of the two-sided 95% confidence interval of the difference between roxadustat and placebo is above 0.

The analysis will be done on the FAS.

Table 20 Primary and sensitivity analysis for change from BL in SF-36 VT subscore to the average in weeks 12 to 28

Code	Set	Endpoint	Method	Covariates
Primary	FAS	SF36-VT Change from Baseline at Weeks 12-28 for all subjects	MMRM	Region, History of CV, visits and visits by treatment as categorical variables. BL Hb , BL SF-36 VT subscore and BL eGFR as continuous covariates.
S1	FAS	SF36-VT Change from Baseline at Weeks 12-28 for subjects with BL VT subscore below 50	MMRM	Region, History of CV, visits and visits by treatment as categorical variables. BL Hb , BL SF-36 VT subscore and BL eGFR as continuous covariates.
S2	FAS	SF36-VT Change from Baseline at Weeks 12-28 for subjects with BL VT subscore equal or above 50	MMRM	Region, History of CV, visits and visits by treatment as categorical variables. BL Hb , BL SF-36 VT subscore and BL eGFR as continuous covariates.

Residual plots will be produced showing the following:

- Model residuals in the y-axis and model predictions in the x-axis,
- Model residuals in the y-axis and baseline SF-36 VT subscore in the x-axis.

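### SAP Table 24 sets the SF-36 Vitality subgroup analysis at Week 28 instead of the tested Weeks 12-28 average and has no row for rescue therapy or eGFR slope, in conflict with the sentence that introduces it

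*SAP*

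**What the plan says.** SAP 7.4.2.9 opens with a general rule: "Each of these key secondary endpoints will also be analyzed by the subgroups of interest" of SAP 7.8, "using only the primary analysis method, descriptively (no hypothesis testing". Table 24 then lists six analyses, A1 to A6. The two SF-36 rows differ in time point: A3 is "SF36-PF Change from Baseline at Weeks 12-28 for all subjects by Subgroup" and A4 is "SF36-VT Change from Baseline at Week 28 for all subjects by Subgroup".

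In the fixed sequence (SAP Table 16), test 4 is "Change from BL in SF-36 Vitality (VT) sub-score to the average VT sub-score of weeks 12 to 28 for all subjects". Test 3 is superiority on use and time to first use of rescue therapy over the treatment period, in the FAS. The annualized eGFR slope is listed as key secondary number 8 but is marked as outside the hierarchy.

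Protocol 7.4.2.2 has a parallel rule, "Each of the key secondary endpoints will be repeated separately by gender, age group, region" and further factors, and leaves the detail of subgroup analyses to the SAP.

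**The concern.** The rule and the table that implements it give different instructions. A programmer working from Table 24 would fit the Vitality model for Week 28 alone and would produce nothing by subgroup for rescue therapy or eGFR slope. A programmer working from the sentence above the table would use the Weeks 12-28 contrast and analyse all eight endpoints.

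The Vitality forest plot is meant to show whether the tested effect is consistent across subgroups. A plot at Week 28 describes a different quantity, so it cannot be set beside the test 4 estimate. Rescue therapy is a sequenced superiority claim, and the need for rescue is a stated secondary objective in both documents. Under Table 24 it would be the only one of the five sequenced claims with no subgroup display. If the gap is noticed only after unblinding, a rescue subgroup analysis or a change to A4 could look prompted by the data.

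**Working it through.** No plan figure has to be reproduced. The check compares Table 24 row by row with the key secondary list (SAP Table 4), the testing sequence (SAP Table 16) and each primary analysis.

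| Key secondary (SAP Table 4) | In fixed sequence | Window or period in primary analysis | Table 24 row | Match |
|---|---|---|---|---|
| 1 Hb | Yes | Weeks 28-36 | A1, Weeks 28-36 | Yes |
| 2 LDL | Yes | Weeks 12-28 | A2, Weeks 12-28 | Yes |
| 3 Rescue therapy | Yes | Treatment period | None | No |
| 4 SF-36 Vitality | Yes | Weeks 12-28 | A4, Week 28 | No |
| 5 SF-36 Physical Functioning | Yes | Weeks 12-28 | A3, Weeks 12-28 | Yes |
| 6 MAP | No | Weeks 20-28 | A5, Weeks 20-28 | Yes |
| 7 Hypertension | No | First occurrence | A6, first occurrence | Yes |
| 8 eGFR slope | No | Slope over treatment | None | No |

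**Counts.** Eight key secondaries less six rows leaves two with no row. Of the five sequenced endpoints, Table 24 covers four, and three of those four keep the tested window.

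**Vitality.** The Weeks 12-28 average appears in Table 4, 6.1.2.4, Table 16, 7.4.2.4 and Table 20, whose primary row is "SF36-VT Change from Baseline at Weeks 12-28 for all subjects". Section 6.1.2.4 builds the average from values "in analysis visit windows at weeks 12 and 28 will be selected" (that sentence names the Physical Functioning score, but the quantity it computes is the Vitality average). The two Vitality subsets by baseline score in Table 20 (below 50; 50 or above) also keep Weeks 12-28. Nothing in the SAP gives a reason for a different contrast in A4. Its analysis set, method and covariates are those of Table 20.

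**Rescue and eGFR slope.** Neither 7.4.2.3 nor 7.4.3.7 specifies a subgroup analysis of rescue therapy, and 7.4.2.8 specifies none for eGFR slope. The footnotes to Tables 24 and 25 restrict certain subgroup factors to certain endpoints, but they exclude neither endpoint. For both, Table 24 shows 0 of the six general factors (age, sex, region, baseline Hb, CV history, baseline eGFR).

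**Protocol status.** Protocol 2.3.2 and 7.4.2.1 list rescue therapy as a key secondary, defined over the first 24 weeks. They do not list eGFR slope, which is in protocol 2.3.3.1 among the additional endpoints. SAP version 5.0 added it to the key list and moved rescue to the whole treatment period.

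**Illustration of precision.** With equal variances at Weeks 12 and 28, complete data and between-visit correlation ρ, the standard error at one visit divided by that of the two-visit mean is 1/√((1+ρ)/2).
- ρ = 0.6: 1/√0.8 = 1.118, about 12% wider intervals.
- ρ = 0.4: 1/√0.7 = 1.195, about 20% wider intervals.

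The documents give no ρ; both values are assumptions. The mismatch between Week 28 and Weeks 12-28 does not depend on them.

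**The case against.** The best reply is that this is a clerical mismatch in a descriptive section. The sentence above Table 24 requires the primary method. For Vitality that is Table 20 at Weeks 12-28, and for rescue it is the Cox model in Table 19. The factors are in Table 25, so a statistician who follows the text could run both analyses correctly. A selective table also has some support: protocol 7.4.1.3 and SAP 7.8 both speak of selected endpoints, and protocol 7.4.2.2 leaves the detail to the SAP.

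Much of this stands. A4 is probably a wrong label, given that the parallel row A3 is right. The revision history suggests that the table was not updated: version 5.0 swapped the two SF-36 scores in the sequence and added eGFR slope, yet Table 24 keeps the old order and lacks the slope. That is an inference, and it does not explain the missing rescue row. The reply does not remove the conflict, because 7.4.2.9 is the specific provision, it covers every key secondary, and its own table does something else.

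A reader might go further in three ways that the documents do not support.
- That no subgroup check of rescue would exist. The introductory sentence commits to one, so the plan contradicts itself; the analysis is not certainly absent.
- That leaving out eGFR slope breaches protocol 7.4.2.2. The slope is a key secondary only in the SAP, so the conflict is internal to the SAP.
- That the plan loses 12% to 20% in precision. Those figures rest on assumed correlations and concern descriptive intervals.

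**Conclusion.** The point holds as an inconsistency between text and table. Of eight key secondaries, five have a Table 24 row that matches the primary analysis, one (Vitality) has a row at the wrong time point and two (rescue therapy, eGFR slope) have no row. The rescue gap matters most, since rescue is test 3 of the sequence and a key secondary in both documents, although over different periods. The eGFR slope is outside the hierarchy and carries no alpha-controlled claim.

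The consequence is limited to descriptive output. Type I error, the fixed sequence and every confirmatory result are unaffected. Whether the wrong Vitality plot appears, and whether the rescue plot is missing, depends on which of the two instructions is followed. This is a minor correction, worth making before unblinding. The conclusion rests on comparing the passages and on no numerical assumption.

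**What to change.** - **Row A4:** change the endpoint to "SF36-VT Change from Baseline at Weeks 12-28 for all subjects", by subgroup, so that it matches Table 20.
- **New row, rescue:** time to first use of rescue therapy, FAS, Cox regression stratified on region and CV history and adjusted for baseline Hb and eGFR as in Table 19. Omit any stratum or covariate that defines the subgroup, as SAP 7.4.1.1.3 already does for the EU primary endpoint. This row follows the SAP's treatment-period definition; note that the protocol defines the endpoint over the first 24 weeks.
- **eGFR slope:** either add a row (FAS, model of 7.4.2.8) or reword the introductory sentence of 7.4.2.9 to say that it is not covered.

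The cost is two or three edited table lines and some extra descriptive output. The models are already specified in the SAP, and no new data are needed.

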7.4.3 Analysis of Additional Secondary Efficacy Endpoints

All the analyses below will be superiority tests. These inferential analyses will be performed on the FAS and presented treatment effect as Roxadustat versus placebo.

Descriptive statistics will be presented by treatment arm.

7.4.3.1 Hb level averaged over weeks 28 to 36, 44 to 52, and 96 to 104 without use of rescue therapy within 6 weeks prior to and during these 8-week evaluation periods

Averaged Hb over weeks 28-36, 44 to 52 and 96 to 104 will be described by treatment arm on the FAS.

The SAS procedure will be similar to the one provided in Section 7.4.2.1

In addition, the number and proportion of subjects with average Hb over weeks 28-36 and over weeks 44-52 and 96-104 and by visit within the <10 g/dL, 10-12 g/dL and >12 g/dL categories will be reported.

7.4.3.2 Time to achieve the first Hb response as defined by primary endpoint for EU (EMA)

Time to achieve the first Hb response, without rescue therapy, will be analyzed using the same methods described in Section 7.4.2.7 on the FAS.

Superiority will be declared if the lower bound of the two-sided 95% confidence interval of the hazard ratio is above 1.

Cumulative incidence will be provided at 4, 8, 16, and 24 weeks with their associated 95% confidence interval reported using Greenwood's formula.

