7 STATISTICAL METHODOLOGY

7.1 General Considerations

- All statistical comparisons will be made using two sided tests at the $\alpha=0.05$ significance level unless specifically stated otherwise. Null hypotheses for superiority testing will be of no treatment difference and corresponding alternative hypothesis will be two-sided. Null hypotheses for non-inferiority testing will be of inferiority of roxadustat treatment and will be one-sided at the $\alpha=0.025$.
- All data processing, summarization, and analyses will be performed using SAS® Version 9.3 (SAS Enterprise Guide 4.3) or higher. Specifications for tables, data listings and figures (TLFs) formats can be found in the TLF Specifications for this study.
- All data will be summarized by treatment arm (roxadustat and placebo) and for the total, unless specified otherwise.
- For continuous variables that are recorded as “< X” or “> X”, the value of “X” will be used in the calculation of summary statistics. The original values will be used for the listings.
- All percentages will be rounded to one decimal place and lined up by the decimal place. The percentage will be suppressed when the count is zero.
- Any p-values will be rounded to four decimal places and will be presented as ‘< 0.0001’ if they are less than 0.0001 after rounding.
- For continuous variables, descriptive statistics will include the number of subjects (n), mean, standard deviation, median, minimum and maximum. Frequencies and percentages will be displayed for categorical data. Percentages by categories will be based on the number of subjects with no missing data, i.e., will add up to 100%. Number of missing values will be shown in the frequencies tables
- All data included in summary tables, inferential analyses or figures will also be listed.
- Listings will be done on all randomized subjects and all assessments (all collected data in the eCRF will be listed except the physical examination data).
- Model checking will be performed using graphical outputs provided by the SAS procedures.

For the definition of subgroups of interest please refer to Section [7.8](#).

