7.4.3.5 Categorical analysis for Hb values

Proportion of Hb values :

The proportion of Hb values within 10-12 g/dL or ≥ 10 g/dL is a quantitative variable in the 0 – 100 range for each subject. Descriptive statistics for this variable will be presented by treatment arm. This variable will be presented in weeks 28-36, in weeks 44-52 and in weeks 96 -104, on the FAS.

Percentage of time during the Efficacy Emergent Period:

Descriptive statistics for the percentage of time with Hb values falling in each interval interval (<10.0 g/dL, within 10.0-12.0 g/dL, > 12.0 g/dL, ≥ 10.0 g/dL, > 13.0 g/dL and > 14.0 g/dL) between the first and last Hb assesment during the Efficacy Emergent Period will be presented by treatment arm.

The number and percentage of subjects, and the number of events, will be reported based on Hb values from the central lab with Hb increase by >2.0 g/dL between any two visits within 4 weeks of treatment.

Time to first occurrence of potential EH will also be analyzed similarly as in Section [7.4.2.7](#) (except that all data during the Efficacy Emergent Period will be taken into account for the analysis). The results will be presented by period (First 6 weeks, Week 7 - Week 27, Week 28 - Week 52 and > Week 52)

7.4.3.6 Occurrence (number) of hospitalizations,number of days of hospitalization per PEY and time to first hospitalization

The number and percentage of subjects with hospitalization will be reported. Descriptive statistics and frequency tabulations by treatment arm of the total duration of hospitalization (days), the average duration of each hospitalization (days), the number of hospitalizations, number of days of hospitalization per PEY and reason for hospitalization will also be reported.

Time to first hospitalization will also be analyzed similarly as in Section [7.4.2.7](#) (except that all data during the Efficacy Emergent Period will be taken into account for the analysis).

Superiority will be declared if the upper bound of the two-sided 95% confidence interval of the hazard ratio of the two treatment arms is below 1. Both descriptive summary and time to first hospitalization will be reported by eGFR category (<15 vs ≥15).

As a sensitivity analysis, the above analysis will be repeated using IPCW method (Appendix 10.7).

The analysis will be done on the FAS.

7.4.3.7 Occurrence and time to first use of rescue therapy during the First 24 Weeks [composite of RBC transfusions, IV iron supplementation and rescue ESA]

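### SAP 7.4.3 sets ungated, unadjusted superiority declarations for 14 additional secondary endpoints without calling them nominal, and the rule for the eight CKD endpoints is reversed

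*SAP*

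**What the plan says.** - **Default level.** SAP 7.1: "All statistical comparisons will be made using two sided tests", at 0.05 unless stated otherwise.
- **Controlled family.** SAP 7.4.2 and Table 16 hold the overall two-sided type I error at 0.05 by a fixed sequence, starting from the EU primary. Key secondary tests 1–5 are in the sequence. Endpoints 6–8 are taken out and expressly left unadjusted.
- **Additional secondary endpoints.** SAP 7.4.3: "All the analyses below will be superiority tests". The next sentence calls them inferential and assigns them to the FAS.
- **Declarations on the upper bound.** For first hospitalization (7.4.3.6), with 1 as the limit that the bound must stay under: "Superiority will be declared if the upper bound of the two-sided 95% confidence interval of the hazard ratio of the two treatment arms". The same sentence appears for rescue in the first 24 weeks (7.4.3.7), RBC transfusion (7.4.3.8), IV iron (7.4.3.9) and ESA (7.4.3.10).
- **Declarations on the lower bound.** For time to first Hb response (7.4.3.2): "Superiority will be declared if the lower bound of the two-sided 95% confidence interval of the hazard ratio is above 1". The same sentence is applied in 7.4.3.16 to all the time-to-event endpoints of 6.1.3.16.
- **Labels used elsewhere.** Key secondary subgroup analyses (7.4.2.9) are done "using only the primary analysis method, descriptively (no hypothesis testing". Sensitivity analyses of both primary endpoints (7.4.1.1.2, 7.4.1.2.2) are also marked as having no hypothesis testing. The word exploratory is kept for hs-CRP and sTFR (6.1.4, 7.4.4) and for the version 1.0 dosing subset (7.9).
- **Protocol.** Section 7.4.3 leaves the methods for these endpoints to the SAP.

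**The concern.** The plan says when an analysis is not confirmatory, but it does not say so in 7.4.3, where it uses the language of formal decision instead. Read literally, one favourable interval among 14 is enough to declare superiority on an outcome such as hospitalization or transfusion, even if the primary or the key secondary sequence has failed.

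Rescue therapy is the clearest case. In Table 16, rescue over the treatment period is test 3, behind the EU primary, Hb and LDL. If LDL fails, the sequence allows no rescue claim. Section 7.4.3 still allows four: the 24-week composite and its three components. The 24-week composite is the Protocol's own key secondary endpoint (Protocol 2.3.2), which the SAP has moved to the additional tier.

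**Working it through.** **1. The plan's own figure.** Under the global null a fixed sequence can err only if its first test rejects, so its family-wise error is 0.05 two-sided. Simulation of 1,000,000 draws gave 0.0500. The stated figure is reproduced for the family it covers.

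**2. Count of explicit declarations.** Six stand in 7.4.3.2 and 7.4.3.6–7.4.3.10. Section 6.1.3.16 defines eight CKD times:
- CKD progression composite
- dialysis, transplant or death
- creatinine doubling
- creatinine doubling, dialysis or transplant
- dialysis or transplant
- ESRD-free survival
- 40% eGFR decrease, dialysis or transplant
- 40% eGFR decrease

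Total 6 + 8 = 14.

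**3. Error per declaration.** Each rule uses one bound of a two-sided 95% interval, so under its null it fires with probability 0.025.

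**4. Independent endpoints.** P(at least one false declaration) = 1 − (1 − 0.025)^m.
- m = 14: 1 − 0.975^14 = 0.298
- m = 9: 1 − 0.975^9 = 0.204

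The second case supposes that Hb response and the four rescue endpoints are truly improved, which leaves hospitalization and the eight CKD times null: 14 − 5 = 9.

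**5. Correlated endpoints.** The documents give no correlations, so these are assumptions. The figures come from simulation of equicorrelated normal statistics, 1,000,000 draws each.

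| Correlation | 14 null | 9 null |
|---|---|---|
| 0 | 0.299 | 0.204 |
| 0.3 | 0.224 | 0.165 |
| 0.5 | 0.175 | 0.134 |
| 0.7 | 0.124 | 0.101 |
| 0.9 | 0.070 | 0.062 |
| 0.95 | 0.054 | 0.049 |

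A block structure (Hb response, hospitalization, four rescue, eight CKD) with correlation 0.5 to 0.95 within blocks and 0 to 0.4 between them gave 0.233 down to 0.111 for 14 nulls, and 0.147 down to 0.067 for 9.

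All these figures treat the rules as pointing the same way. Under independence direction makes no difference. Under positive correlation, the CKD rules as printed point against the others, which would raise the chance of at least one false declaration. That was not computed.

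**6. Direction of the CKD rule.** Section 7.4.3.16 uses the methods of 7.4.2.7, where the hazard ratio is roxadustat relative to placebo. The CKD events are all adverse, so benefit means a ratio below 1. The printed rule needs the lower bound above 1, which is a significant excess of events on roxadustat. The same wording is right in 7.4.3.2, where the event is a response.

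**The case against.** **No stated error rate is broken.** This stands. The 0.05 in SAP 7.4.2 belongs to the EU primary and the key secondary sequence. The Protocol puts these endpoints a tier lower (2.3.3, Other Endpoints), and so does the SAP (Table 5). A reader might infer that the trial's overall type I error control fails. The documents do not support that.

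**The error rate can be overstated.** This also stands. A reader might take the two-sided figure, 1 − 0.95^14 = 0.51, as the chance of a false superiority claim. Half of each test's 0.05 lies in the direction that cannot trigger its rule. The all-null case is also unlikely: Hb response is planned at 65% versus 25%, and the Protocol's amendment rationale expects superiority on rescue. The eight CKD times share components, so high correlation is credible.

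**Not every item in 7.4.3 is a test.** Correct. LDL below 100 mg/dL, the blood pressure goal, EQ-5D, WPAI and PGIC are descriptive, so the opening sentence is broader than its content. The count of 14 uses only explicit rules.

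**A chance claim of slower CKD progression.** A reader might infer this risk too. As printed, the rule cannot produce it; only apparent harm can.

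**The rescue endpoints are prespecified.** True, and a 7.4.3 result does not reopen Table 16. But prespecification does not make an ungated declaration nominal, and the SAP's silence here contrasts with its explicit labels elsewhere.

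**Conclusion.** The point holds as a labelling and decision-rule defect, not as a failure of the confirmatory plan. Fourteen declarations stand outside the controlled family with no gate, adjustment or nominal status.

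With all 14 null, the chance of at least one false declaration is about 0.30, 0.17 and 0.07 at correlations 0, 0.5 and 0.9. In the more realistic nine-null case it is about 0.20, 0.13 and 0.06, or roughly 8, 5 and 2.5 times the 0.025 of a single rule. These sizes rest on assumed correlations and on rules taken to point the same way. At very high correlation the excess over a single rule is modest.

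The reversed CKD rule is a separate error. It rests on the text alone and needs no assumption.

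**What to change.** 1. In SAP 7.4.3, replace the opening sentence with a statement that additional secondary endpoints lie outside the type I error control of the EU primary and key secondary tests 1–5, and are reported with estimates, 95% confidence intervals and nominal p-values, with no confirmatory superiority claim.
2. Remove or reword the declaration sentences in 7.4.3.2, 7.4.3.6–7.4.3.10 and 7.4.3.16.
3. If 7.4.3.16 keeps a direction of benefit, make it the upper bound of the hazard ratio (roxadustat relative to placebo) below 1.
4. Add any endpoint wanted for a formal claim after test 5 in the Table 16 sequence.

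This changes SAP wording only, and tests 1–5 lose no power. The sponsor gives up unadjusted superiority language for these endpoints, and an endpoint added after test 5 can be claimed only if every earlier test succeeds.
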